### 10.3 Recording of Adverse Events

At each contact with the subject, the investigator must seek information on adverse events by specific questioning and, as appropriate, by examination. Information on all adverse events should be recorded immediately in the source document, and also in the appropriate adverse event module of the case report form (CRF). All clearly related signs, symptoms, and abnormal diagnostic procedures results should be recorded in the source document, though should be grouped under one diagnosis.

All adverse events occurring during the study period must be recorded. The clinical course of each event should be followed until resolution, stabilization, or until it has been determined that the study treatment or participation is not the cause. Serious adverse events that are still ongoing at the end of the study period must be followed up to determine the final outcome. Any serious adverse event that occurs after the study period and is considered to be possibly related to the study treatment or study participation should be recorded and reported immediately.

### 10.4 Reporting of Serious Adverse Events

#### 10.4.1 IRB Notification by Sponsor-Investigator

Reports of all events (including follow-up information) that meet the definition of an unanticipated problem posing risk to subjects or others must be submitted to the IRB within one week (5 business days) following the occurrence of the unanticipated problem or the principal investigator's acquiring knowledge of the unanticipated problem in accordance with IRB policy.

Additionally, the sponsor-investigator will submit a summary of all Unanticipated problems that occurred since the beginning of the study at the time of continuing review. Copies of each report and documentation of IRB notification and receipt will be kept in the Regulatory binder.

#### 10.4.3 FDA Notification by Sponsor-Investigator

The Columbia University Medical Center Sponsor-Investigator, as holder of the IND, will be responsible for all communication with the FDA. Columbia University Medical Center Principal Investigator will report to the FDA, regardless of the site of occurrence, any adverse event that is serious, unexpected and there is evidence to suggest a causal relationship between the drug and the adverse event. These must be reported to the FDA and any affiliate sites as soon as possible, but in no case later than 15 calendar days after the sponsor determines that the information qualifies for reporting. The Sponsor-Investigatro will also submit an IND annual report to the FDA in accordance with 21.CFR 312.33.

The Columbia University Medical Center Sponsor Investigator must report to the FDA and any affiliate site investigators as follows:

- Any unexpected fatal or life-threatening event must be reported as soon as possible, but no later than 7 calendar days after the sponsor investigator initial receipt of the information
- Any findings from epidemiological studies, pooled analysis of multiple studies, or clinical studies, whether or not conducted under an IND, and whether or not conducted by the sponsor-investigator, that suggest a significant risk in humans exposed to the drug must be reported as soon as possible but no later than 15 calendar days after the sponsor-investigator determines that the information qualifies for reporting
- Any findings from animal or in vitro testing whether or not conducted under an IND, and whether or not conducted by the sponsor-investigator, that suggest a significant risk in humans exposed to the drug must be reported as soon as possible but no later than 15 calendar days after the sponsor-investigator determines that the information qualifies for reporting
- Any clinically important increase in the rate of a serious suspected adverse reactions over that listed in the protocol or Investigator Brochure
- Expected SAEs and AEs will be included in the IND Annual Reports.

Follow-up information to a safety report should be submitted as soon as the relevant information is available. However, if the results of a sponsor's investigation show that an adverse drug experience not initially determined to be reportable are so reportable, the sponsor investigator must report such experience as soon as possible, but no later than 15 calendar days after the determination is made.

All other serious unexpected experiences associated with the use of the study treatment will be reported to FDA as soon as possible but in no event later than 15 calendar days after initial receipt of the information.

#### 10.4.4 DSMC Reporting by the Sponsor Investigator

Serious adverse events not constituting unanticipated problems are to be reported to the HICCC DSMC. Reporting should occur within 24 hours of knowledge of the SAE occurring at our institution or affiliate sites.

#### 10.4.5 Reporting to Drug Manufacturer by Sponsor-Investigator

The Sponsor-Investigator will report to investigational agent manufacturer any serious adverse events that meet the reporting criteria to the Institutional Review Board as described in section 10.4 and/or to the FDA as described in section 10.4 within **24 hours/1 business day** of becoming aware of it, so that these reports can be evaluated and included in the Investigator's Brochure and for IND safety submissions per regulations. Reporting will occur by sending the reporting form along with any additional documentation sent to the regulatory authorities.

The initial report must be as complete as possible, including an assessment of the causal relationship between the event and the investigational product(s), if available. Information not available at the time of the initial report (e.g., an end date for the adverse event or laboratory values received after the report) must be documented on a follow-up report. A final report to document resolution of the SAE is required. The Syndax tracking number and the institutional protocol number should be included on SAE reports (or on the fax cover letter) sent to Syndax. A copy of the fax transmission confirmation of the SAE report to Syndax should be attached to the SAE and retained with the patient records

Syndax Drug Safety Contact Information:

**Email:** [contact]

**[contact]

At the time of IRB renewal or at the request of the manufacturer, the Sponsor- Investigator will submit a summary of all Serious Adverse Events that have occurred inclusive of all sites to manufacturer.

#### 10.5 Reporting Process

Adverse events may be submitted on FDA Form 3500A, the HICCC DSMC Serious Adverse Event Reporting Form, or in a narrative format. If supplied as in a narrative format, the minimum information to be supplied is noted above at the beginning of section 10.

## **11. STATISTICAL CONSIDERATIONS**

### **11.1 Study Design**

This is a Phase II, multicenter, open label, single arm study. Eligible patients will be enrolled according to Simon's two-stage design as described below. Objective response to treatment will be assessed using RECIST criteria until progression or intolerable toxicities occur, necessitating cessation of treatment.

### **11.2 Study Endpoints**

#### *Primary Efficacy*

- Objective response rate (CR or PR) based on the patient's best response that is documented during administration of the study drug.

#### *Secondary Efficacy*

- Duration of response for patients who achieve CR or PR
- Duration of overall survival
- Duration of progression-free survival

#### *Safety*

- Incidence, severity, and duration of adverse events, including serious events and those considered by the investigator to be related to protocol therapy

### **11.3 Sample Size Considerations**

#### **11.3.1 Initial Protocol**

Up to 40 patients may be enrolled to achieve 32 response-evaluable patients. It's anticipated that no more than 25% of enrolled patients will be non-evaluable for response.

The sample size for the expansion phase is based on a Simon 2-stage design (optimum version) and objective response rate endpoint described in Section 11.2. To calculate the required sample size, the following assumptions were made. The response probability of an ineffective therapy in this indication (i.e., the uninteresting response level) was chosen to be 15%; the response probability of an effective therapy (i.e., the targeted response level) was chosen to be at least 35%, level of significance of 10%, and power of 80%. Based on these

assumptions, the sample size of the first and second stage is 9 and 14, respectively, for a total of 23 response-evaluable patients (see below).

- If less than 2 of the 9 patients achieve an objective response (CR or PR) during the first stage of the study, enrollment will be terminated for unselected patients and entinostat will be declared to have insufficient activity in this indication in unselected patients. Thereafter, enrollment will be restricted to patients whose tumors display the characteristic master regulator expression profile consistent with hypothesized entinostat sensitivity.
- If 6 or more unselected patients achieve objective response after completion of the second stage, then entinostat will be considered sufficiently promising in this treatment setting and may be evaluated in future studies.
- If the total number of patients with objective response after completion of the second stage is between 2 and 5, further development of entinostat in this indication will be assessed. If the true objective response rate for entinostat is  $\leq 15\%$ , then the expected sample size is 14.61 patients, with probability of terminating the study at the end of the first stage equal to 60%.

Up to 40 patients may be enrolled to achieve 32 response-evaluable patients (9 unselected patients in stage 1, and 23 selected patients in stage 1 and 2).

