### **2.3.2 Entinostat (SNDX-275) induces *in vivo* inhibition of HST-S cells**

We validated three compounds in H-STS xenograft models in collaboration both with Champions Oncology and with the [name]'s lab at Columbia. These compounds included entinostat, tivantinib, and belinostat, predicted to have high, low, and negligible potency respectively in reverting activity of patient specific MR proteins. Assays from both labs confirmed that entinostat produced significant tumor size reduction over 25 days, while tivantinib had only a modest effect (40% viability reduction compared to DMSO, as predicted) and belinostat was indistinguishable from DMSO treated controls, also as predicted. Consistent with the analysis, entinostat activity was virtually identical at two different doses. From this analysis, considering that activity of the drugs was prioritized purely based on patient derived data and that cell line assays were used strictly to assess compound mechanism of action, in term of targeting critical MR proteins, we estimate that a minimum of 10% of GEP-NET patients should be highly sensitive to entinostat.

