### 3.3 Number of Patients

Up to 40 patients with relapsed or refractory abdominal neuroendocrine tumors may be enrolled to achieve up to 32 response-evaluable patients. Safety will be evaluated in an ongoing fashion. It is anticipated that no more than 25% of enrolled patients will be non-evaluable for response.

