## 5. PATIENT ENROLLMENT

All patients will be screened by the study site's principal investigator or one of the study site's sub-investigators prior to entry on this study. An explanation of the study and discussion of the potential risks and benefits will be fully disclosed to the patients prior to the screening process in

order for the patient to provide a voluntary written informed consent. Only eligible and consenting patients will be entered into the study.

The screening period for a patient commences when the patient signs the informed consent form. The consent form must be signed before any study-specific tests are performed.

The IRB / EC of an institution must approve the consent form document to be used at the center prior to its local activation; changes to the consent form during the course of the study will also require IRB / EC notification/approval.

Patients who cannot give informed consent (i.e. mentally incompetent patients, or those physically incapacitated such as comatose patients) are not to be recruited into the study. Patients competent but physically unable to sign the consent form may have the document signed by their legal guardian. Each patient will be provided with a full explanation of the study before consent is requested.

**All participants must be centrally registered through the Central Registration Office within Herbert Irving Comprehensive Cancer Center at CUMC prior to initiation of study treatment.**

Registration hours are available Monday through Friday from 9:00am – 5:00pm EST (excluding holidays and weekends). Same day patient registrations (and after hour registrations) will be accommodated on a case by case basis provided that the study team has expressed all time sensitive registration concerns/cases in a timely manner to the Central Registration Office.

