Upon receipt of the above mentioned documentation, participant eligibility information will be verified by a qualified Central Registration Registrar. If any questions arise during the review process, queries in the form of emails will be addressed to the applicable study team personnel for clarification prior to enrollment. All applicable finalized registration/eligibility information will then be entered into HICCC’s institutional CTMS database by the Central Registration Registrar.

Upon completion, an official subject registration notification email will be sent to the PI/research team which will include eligibility/enrollment status, as well as subject ID information. Protocol therapy may not be initiated prior to receipt of this notification from the Central Registration Office.

All screen fail/ineligible subjects, as well as subject's who withdraw consent prior to enrollment/initiation of protocol therapy must be submitted to the Central Registration office in a manner analogous to the procedures noted above. Applicable source documentation will be required within the corresponding submissions.

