## 11.5 Planned Methods of Analysis

The full analysis set (FAS) population will include all patients who are enrolled in the study. A patient is considered enrolled in the study once the patient or legal representative grants written informed consent. The FAS population will serve as the population for a supportive analysis of the primary efficacy analysis.

The per-protocol population (evaluable patients) will serve as the population for the primary analysis of the efficacy data in this study. The per-protocol population is a subset of the FSA population and will include patients who meet all of the following criteria:

- Complete at least **two** cycles of entinostat therapy, irrespective of dose level.
- Undergo CT scans at Screening and day 1 of cycle 3.

The safety population consists of all patients who receive at least one dose of study drug. At least one laboratory or vital sign measurement obtained subsequent to at least one dose of study drug is required for inclusion in the analysis of each safety specific parameter. To assess change from baseline, a baseline measurement is also required.

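### At the plan's 25% upper bound, 40 enrolled give 30 evaluable patients rather than 32, and Section 11.5's definition of enrolment at consent conflicts with how the rest of the protocol uses the term

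*Combined protocol and SAP*

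**What the plan says.** **Size.** Section 11.3.1 states: "Up to 40 patients may be enrolled to achieve 32 response-evaluable patients". It adds: "It's anticipated that no more than 25% of enrolled patients will be non-evaluable for response". The synopsis and Section 3.3 carry the same three figures. The 32 is made up of "9 unselected patients in stage 1, and 23 selected patients in stage 1 and 2". That make-up belongs to one branch of the design: if fewer than 2 of the first 9 evaluable patients respond, enrolment of unselected patients ends and only profile-positive patients enter from then on.

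**Definition of enrolment.** Section 11.5, in defining the full analysis set (FAS), says: "A patient is considered enrolled in the study once the patient or legal representative grants written informed consent". The FAS is the population for a supportive analysis of the primary endpoint; the primary analysis uses the evaluable (per-protocol) patients.

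**Order of events.** Section 5 requires that "The consent form must be signed before any study-specific tests are performed". Under Section 4.1, criterion 2, the profile is read from a fresh biopsy taken during screening, so after consent.

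**Competing usage.** The central registration procedures in Section 5 describe patients who "withdraw consent prior to enrollment/initiation of protocol therapy", which places enrolment after consent. Appendix 5, item 5, uses the same order.

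**Prevalence.** Section 2.3.1 reports that about 10% of a metastatic GEP-NET cohort had master regulator overlap of at least 75% with the hepatic-metastasis cell lines. Section 2.3.2 gives a floor for sensitivity: "we estimate that a minimum of 10% of GEP-NET patients should be highly sensitive to entinostat". The profile cut-off for eligibility is not stated.

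**The concern.** An allowance for non-evaluable patients should cover the worst loss that the plan anticipates. This one does not: the cap of 40, the target of 32 and the 25% bound cannot all hold at the bound.

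The definition in Section 11.5 is a separate problem. It is the only explicit definition of enrolment in the document, and the cap of 40 is expressed in enrolled patients. If the two are read together, patients who consent, are biopsied, prove profile-negative and never receive drug use up places under the cap. They would also sit in the denominator of the supportive response rate. The cohort at stake is the selected one, which tests the hypothesis of a sensitive subset.

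**Working it through.** **1. Reproduce the stated 40.** Inputs from Section 11.3.1: target 32 evaluable, loss d up to 25% of enrolled.

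- Correct inflation, N/(1 − d): 32/0.75 = 42.7, so 43.
- Multiplying instead, N × (1 + d): 32 × 1.25 = 40, which matches the stated figure.
- N/(1 − d) also gives 40 at d = 20% (32/0.80), but the plan states 25%.
- Yield of 40 at the bound: 40 × 0.75 = 30. Largest loss compatible with 32: 1 − 32/40 = 20%, or 8 patients.

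The Simon figures are not at fault. An exact binomial search for the optimal design (15% versus 35%, alpha 10%, power 80%) returns at most 1 of 9 to stop and at most 5 of 23 to reject. It has alpha 0.099, power 0.804, early-termination probability 0.599 and expected size 14.61, which agrees with the plan.

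**2. By branch, at 25% loss.**

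- Stage 1 passes: 23 unselected evaluable need 23/0.75 = 30.7, so 31 enrolled. This fits within 40.
- Stage 1 fails: 9/0.75 = 12 and 23/0.75 = 30.7, so 31; together 43. With 40, the selected cohort gets (40 − 12) × 0.75 = 21 evaluable, against 23.

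The failing branch has probability 60% at a true response rate of 15% (the plan's figure) and about 12% at 35% (computed: 0.121).

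**3. Literal consent counting in the failing branch.** Twelve consents go to stage 1 (ordinary screen failures ignored), leaving 28. Profile-positive = 28 × prevalence; evaluable = that × 0.75; consents needed for 23 evaluable = 23/(prevalence × 0.75). The 10% row takes the Section 2.3.1 figure as an assumption for this population; 20% and 30% are assumed.

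| Prevalence | Profile-positive among 28 | Evaluable | Needed evaluable | Consents needed |
|---|---|---|---|---|
| 10% | 2.8 | 2.1 | 23 | 307 |
| 20% | 5.6 | 4.2 | 23 | 154 |
| 30% | 8.4 | 6.3 | 23 | 103 |

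The result is not sensitive to the exact prevalence. With no evaluability loss at all, 40 − 9 = 31 consents remain, and prevalence would have to reach 23/31 = 74% to expect 23.

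**4. Effect on the FAS under the same reading.** At 10% prevalence, about 28 − 2.8 = 25.2 of the 40 FAS patients (63%) would be profile-negative and untreated. They would be counted in the denominator of the supportive response rate with no chance of contributing a response to drug.

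**5. Later-step reading.** If enrolment follows confirmed eligibility and profile, screen failures do not count toward the 40, and step 3 has no effect on the cap. As a sizing error, only 40 versus 43 remains. The screening load is still unstated.

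**The case against.** Three points on the other side have force.

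First, 25% is a ceiling, and Section 3.3 speaks of up to 32. A reader might infer that the planned size cannot be delivered at all. The documents do not support that: at a loss of 20% or less, 40 give 32, and if stage 1 passes, 40 is ample even at 25%. The shortfall is 2 evaluable patients, at the bound, in one branch.

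Second, a reader might infer that the selected cohort would close with a handful of patients. That carries an analysis-set definition into the sample-size section, whose wording does not fit it. Section 11.3.1 restricts enrolment to profile-positive patients, which is impossible if enrolment means consent, because consent precedes the biopsy. Nor can a non-evaluable share of at most 25% of those enrolled coexist with consent counting when perhaps 90% of those screened are profile-negative. Section 5 and Appendix 5 also place enrolment after eligibility review. So the intended reading is probably the later step. What stands is the conflict: the only explicit definition says otherwise, and it also governs the FAS.

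Third, 10% should not be taken as the prevalence of eligibility. Section 2.3.1 describes overlap with particular cell lines, Section 2.3.2 gives a minimum for sensitivity, and no cut-off is stated. The table is therefore a range of assumptions, although its conclusion holds well beyond that range.

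**Conclusion.** The point holds in two parts.

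- **Arithmetic.** The figures 40, 32 and 25% are inconsistent at the stated bound: 30 evaluable instead of 32, or 43 enrolled instead of 40. The consequence is confined to the branch where stage 1 fails, where 21 selected evaluable patients would be available against the 23 that the Simon design requires. On its own this is minor.
- **Definition.** Section 11.5 conflicts with Sections 5 and 11.3.1 and Appendix 5. Its literal effect is large: about 2, 4 or 6 selected evaluable patients against 23 at assumed prevalences of 10%, 20% or 30%, and a supportive response rate diluted by untreated patients. The cap effect is the consequence of one reading, not a forecast, and it disappears under the later-step reading. The FAS wording is wrong as written until it is changed.

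The results rest on 25% loss in both cohorts, 12 consents for stage 1 with no other screen failures, and the prevalences shown.

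**What to change.** In the synopsis, Section 3.3 and Section 11.3.1, state that 40 enrolled supports 32 evaluable only if no more than 20% (8 of 40) are non-evaluable. State also that at 25% it yields 30, which leaves 21 selected evaluable patients, short of the required 23, and that 43 would be needed. If 20% is adopted as the planning rate, give a reason for it beyond the fact that it fits the cap.

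In Section 11.5, define enrolment as central registration once eligibility, including profile where required, is confirmed (or as first dose). Apply both the cap of 40 and the FAS to that count. Report consented and profile-screened patients separately, and give the expected number to be screened for the selected cohort with the prevalence assumed.

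The cost is wording in four places and one definition. Raising the cap to 43 would add three patients. The screening estimate adds no work to the trial, but it makes visible a biopsy and sequencing load, on the order of 100 to 300 consents at the prevalences above, that the plan does not now budget for.
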